I will allow the Sponsor, ARS Pharmaceuticals Inc. (ARS) and its agents, as well as the United States (US) Food and Drug Administration (FDA) and other regulatory agencies to inspect study facilities and pertinent records at reasonable times and in a reasonable manner, ensuring subject confidentiality. If I am notified that this study is to be inspected by a regulatory agency, I will notify the Sponsor as soon as possible thereafter (no later than one week).

This protocol contains information that is proprietary to ARS. The information contained herein is provided for the purpose of conducting a clinical trial for ARS.

The contents of this protocol may be disclosed to study personnel under your supervision and to your IRB/EC. The contents of this protocol may not be disclosed to any other parties (unless such disclosure is required by government regulations or laws) without the prior written approval of ARS.

Investigator's Signature

Date

PROTOCOL SYNOPSIS

| | | |
|--------------|--|---|
| Study Title | A Single-Dose, Randomized, Placebo-Controlled, Cross-Over Study of the Safety and Efficacy of Intranasal Epinephrine After Administration of ARS -1 in Subjects with Frequent Urticaria Flares (EPI U01) | |
| Phase | Phase 2 | |
| Study Drug | ARS-1 (Intranasal [IN] Epinephrine) | |
| Objectives | Intramuscular (IM) epinephrine injection is indicated in the emergency treatment of allergic reactions (Type I) including anaphylaxis. Both IM and subcutaneous (SC) dosing of epinephrine is approved by the Food and Drug Administration (FDA) as efficacious in product labeling in the United States (US). Epinephrine injection is also recommended in medical prescribing guidelines in the US for the management of acute flares with associated angioedema in patients with urticaria. Acute urticaria is treated with but often unresponsive to antihistamines and corticosteroids. IM epinephrine is typically efficacious in alleviating urticarial flares. An epinephrine nasal spray (ARS-1) is being developed for patients as a needleless alternative route of epinephrine administration for the treatment of urticarial flares. The objectives and endpoints of this study are as below. | |
| | Objective | Endpoints |
| | Primary | |
| | To determine the effect of ARS-1 versus placebo based on a patient reported pruritus/hive score | 
A patient reported pruritus/hive scorePatient reported pain associated with the urticaria flair based on visual analog scale (VAS) |
| | To assess time to effect and duration of effect on acute flares associated with urticaria based on a patient reported pruritus/hive score. | 
An investigator-rated extent of urticaria; % of body area with urticariaAn investigator-rated erythema score |
| | Secondary | |
| | To assess the safety and tolerability of ARS-1 in subjects with urticaria after IN administration of epinephrine. | 
Adverse events (AEs)Vital signs |
| | [REDACTED] | |
| Study Design | This is a Phase 2, single-dose, randomized, placebo-controlled, crossover study that will consist of a screening period and an open-label treatment period. Subjects enrolled will have acute urticaria with known etiology or have chronic spontaneous urticaria with unknown etiology at least two (2) times a week while on a chronic treatment. | |
| | Each subject will be randomized to receive either a single treatment of ARS-1 (1 mg and 2 mg dose) or placebo nasal spray and then will be crossed over to receive other treatments | |

| | |
|--------------------------------|---|
| | 
during an acute urticaria flare. Efficacy will be primarily assessed using a patient reported pruritus/hive score and VAS for pain. Clinical assessments will also be conducted by the Investigator after dosing ARS-1.
 
Approximately 32 eligible male or female subjects, 18 to 65 years of age, with urticaria who experience acute flares while on a chronic treatment regimen or chronic spontaneous urticaria with unknown etiology at least two (2) times a week will be randomized to receive ARS-1 (1 mg dose), ARS-1 (2 mg dose) or placebo. After screening subjects will return to the clinical site when experiencing an acute flare of urticaria symptoms or chronic spontaneous urticaria.
 
Screening Period: Subjects will be screened to assess eligibility for the clinical trial. All subjects will undergo safety screening evaluations within 90 days prior to treatment.
 
Open-Label Treatment Period: Subjects will return to the site when experiencing an acute flare of urticaria symptoms or chronic spontaneous urticaria before taking other acute medications. Urticaria symptoms and severity will be assessed based on both patient-reported and clinician-based assessments. After baseline safety assessments, subjects will be randomized to receive the following treatments at each of the three Treatment Periods:
 
 • 1 mg per 100 microliters (µL) dose of ARS-1, • 2 mg per 100 µL dose of ARS-1, or • placebo (100 µL) 
If possible, rescue medication should be avoided for 15 minutes after dosing. Subjects will be monitored for both safety and symptom relief. Safety assessments will be performed after dosing and will include AEs and vital signs. Concomitant medications will be recorded.
 
Subjects should remain in the clinic as below.
 
 - Acute flare: at least 2 hours after dosing and can discharge when the discharge criteria is met (the time when symptoms of acute urticaria have been effectively treated based on the Investigator's or his/her designee's opinion will be recorded, not necessarily when subjects discharged). If no relief of pruritus symptoms after 2 hours, other acute interventions may be administered as rescue. - Chronic spontaneous urticaria: until the urticaria symptoms returns to the baseline. If the time to return to baseline is beyond 4 hours, such time may be recorded by the patient and reported in the follow-up call. 

 |
| Sample Size | 32 subjects (urticaria patients) |
| Study Population | Adult volunteers aged 18 to 65 years diagnosed with urticaria who experience an acute flare of symptoms or have chronic spontaneous urticaria at least two (2) times a week while on a chronic treatment regimen. |
| Main Inclusion Criteria | 
For a subject to be eligible for this study, he or she must meet all of the following criteria:
 
 1. Is a male or female subject between the ages of 18 and 65 years, inclusive. 2. Has been clinically diagnosed with acute flares or with chronic spontaneous urticaria with unknown etiology and have urticaria symptom (patient-rated pruritus and hive severity score ≥ 2) at least two (2) times a week while on a chronic treatment (e.g., |

| | |
|--------------------------------|--|
| | 
antihistamine) at least 2 weeks before dosing and will remain the same throughout the study.
 
 Has body weight more than 30 kilogram (kg) and body mass index between 18 and 34 kg/m², inclusive. Has no medical history of hypertension and cardiovascular disease in the last 10 years. Controlled hypertension without beta blocker confirmed by the Investigator is acceptable. At screening, has stable vital signs in the following ranges (after 5 minutes of rest): 
 Systolic blood pressure (SBP) ≥ 90 and ≤ 140 mmHg Diastolic blood pressure (DBP) ≥ 50 and ≤ 90 mmHg Heart rate (HR) ≥ 45 and ≤ 100 beats per minute (bpm) 
Note: Each blood pressure (BP) should be taken after at least 5 minutes rest in a chair with back supported, legs uncrossed, and upper arm bared (slight recline for comfort is permitted). If vital signs are out of range, the Investigator may obtain two additional readings, so that up to 3 consecutive assessments are made within 1 hour.
 If female, is not pregnant or breastfeeding based on the following: 
 agree to the use of highly effective contraceptive methods for at least 2 weeks before baseline until 7 days after the last day of study drug and a negative urine pregnancy test at baseline; or is of nonchildbearing potential defined as clinically infertile as the result of surgical sterilization (hysterectomy, bilateral tubal ligation, bilateral salpingectomy and/or bilateral oophorectomy); or is confirmed postmenopausal status (defined as either having amenorrhea for ≥ 12 consecutive months without another cause and documented serum follicle-stimulating hormone (FSH) level > 40 mIU/mL or another documented medical condition (e.g., was born without a uterus)). 
NOTE: The following are considered highly effective contraceptive methods: abstinence, hormonal oral contraceptives, injectables, and patches; intrauterine devices; double-barrier methods (synthetic condom, diaphragm, or cervical cap used with spermicidal foam, cream, or gel); Nexplanon contraceptive implant (if implanted within 3 years); and male partner sterilization.
 If male (with or without vasectomy), agree to the use of highly effective contraceptive methods (as listed in Criterion #6 above) at screening until 7 days after the last day of study drug. Is able to communicate clearly with the Investigator and staff; able to read, complete questionnaires, and understand study procedures. Is willing and able to provide written informed consent prior to participating in the study. |
| Main Exclusion Criteria | 
Subjects must NOT meet any of the following Exclusion criteria to be eligible for enrollment:
 
 Has a history of clinically significant gastrointestinal, renal, hepatic, neurologic, hematologic, endocrine, oncologic, pulmonary, immunologic, psychiatric, or cardiovascular disease or any other condition which, in the opinion of the Investigator, would jeopardize the safety of the subject or impact the validity of the study results. Patients receiving beta blocker due to potential interaction with the study drug. Has prior nasal fractures, severe nasal injuries or history of nasal disorders (e.g., polyps, polyposis, recurrent epistaxis [>1 nosebleed per month], clinically meaningful deviated septum, nasal piercing or any nasal passage abnormality based on the Investigator's judgement). Has any clinically significant medical condition or physical exam (PE) finding as deemed inappropriate by the Investigator. Has abnormal cardiovascular exam at screening including any prior history of myocardial infarction or clinically significant abnormal electrocardiogram (ECG) (e.g., |

| | |
|--|--|
| | 
second- or third-degree heart block, uncontrolled arrhythmia, QTcF [Fridericia's correction] interval >450 msec for male subjects and >470 msec for female subjects).
 
 Has mucosal inflammatory disorders (e.g., pemphigus or Sjogren's syndrome or fungal sinusitis). Has had significant traumatic injury, major surgery, or open biopsy within 30 days prior to study screening. Has donated blood or had an acute loss of blood (>50 milliliter [mL]) during the 30 days before study drug administration or intends to donate blood or blood products within 30 days after the completion of the study. Known hypersensitivity to any compound in the test product, or any other closely related compound (e.g., dihydropyridine-derived molecules). Has participated in a clinical trial within 30 days prior to the first dose of study drug. Participation in an observational (non-interventional) study is not excluded as long as there are no scheduling conflicts with this study. Has had treatment with any epinephrine or norepinephrine containing products within 7 days of Day -1. At screening is positive for human immunodeficiency virus (HIV), Hepatitis B surface antigen (HbSAg), or Hepatitis C, or a positive urine screen for drugs of abuse or cotinine, or a positive saliva test for alcohol. Has an immediate family member of the Investigator, or an employee of the study center, with direct involvement in the proposed study, or other studies under the direction of the Investigator or study center or is in a dependent relationship with a study center employee who is involved in the conduct of this study (e.g., spouse, parent, child, sibling), or may consent under duress. |
| Dosage and Administration of Study Drug | 
The ARS-1 dose of epinephrine by IN administration in this study is 1 mg and 2 mg per dose delivered in a volume of 100 µL aqueous solution. The side (right or left) of the dosing will be alternated per randomization. ARS-1 or placebo will be dosed to the nostril by the medical professional in a clinical setting. Subjects may be in a semi-supine position prior to dosing, at the time of dosing and throughout the first 120 minutes after dosing.
 |
| Efficacy Assessments | 
The following efficacy assessments will be evaluated based on self-reported and clinical assessments of pruritus at pre-dose, and at 5 (± 2 min), 10 (± 2 min), 15 (± 3 min), 30 (± 5 min), 45 (± 5 min), 60 (± 10 min), 120 (± 10 min) minutes and every 60 minutes (± 10 min) after dosing until the discharge criteria (the time when symptoms of acute urticaria have been effectively treated based on the investigator's or his/her designee's opinion will be recorded, not necessarily when subjects discharged) is met for acute flare and until urticaria symptoms returns to the baseline for chronic spontaneous urticaria. [REDACTED]
 
[REDACTED] The actual time of the assessment and of when the symptoms return to the baseline will be recorded. Subjects should also record the date and time of recurrence, if any, of symptoms after they leave the clinic.
 
 A patient reported pruritus/hive score from 0 (none) to 3 (severe) for itch and hive using Uniform Assessment System (UAS) twice daily Patient reported pain associated with the urticaria flare will be recorded based on a self-reported VAS score An investigator-rated extent of urticaria; % of body area with urticaria (Grade 1: urticarial lesions covering < 10% body surface area [BSA]; Grade 2: urticarial lesions covering 10-30% BSA; Grade 3: urticarial lesions covering > 30% BSA) An investigator-rated erythema score (0 = none, 1 = almost clear [slight redness], 2 = mild erythema [definite redness], 3 = Moderate erythema (marked redness), 4 = |

| | |
|-----------------------------|---|
| | 
severe erythema [fiery redness])
 
[REDACTED]
 
[REDACTED]
 
[REDACTED]
 
[REDACTED]
 
[REDACTED]
 |
| Safety Analysis | 
AEs will be collected and reviewed to evaluate the safety and tolerability of ARS-1. AE collection will begin after dosing and continue until discharge. AEs may be either spontaneously reported or elicited during questioning and examination of a subject. AE information will be elicited at appropriate intervals by indirect questioning using a non-leading question.
 
Vital signs measurement (BP, pulse rate [PR], respiratory rate, and temperature will be taken at pre-dose, and at 5 (\pm 2 min), 20 (\pm 2 min), 30 (\pm 2 min), 60 (\pm 5 min) and 120 (\pm 5 min) minutes after dosing.
 
Actual reading times at the measurement by hour/minutes/seconds will be recorded.
 |
| Statistical Analysis | 
All quantitative endpoints will be analyses using linear mixed models with fixed effects for treatment and period and a random effect for subject. For each endpoint, the following comparisons will be made using two-sided tests at the $\alpha=0.05$ level of significance:
 
 1 mg ARS-1 vs Placebo 2 mg ARS-1 vs Placebo 
There will be no adjustments for multiplicity; hence, all analyses will be viewed as exploratory and hypothesis generating, rather than confirmatory.
 |
| Study Duration | 
It is anticipated that each subject will participate in the study for up to 120 days, which comprises a 90-day screening period and 3-4-week study period during which three acute flares of urticaria symptoms will be treated.
 |
| Study Centers | 
Up to Four (4) Centers
 |

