3.1.1 Randomization/Assignment to Study Drug

subjects with urticaria who experience acute flares while on a chronic treatment regimen or chronic spontaneous urticaria with unknown etiology at least two (2) times a week will be enrolled and randomized to receive the following treatments in each Treatment Period:

- 1 mg/100 μ L dose of ARS-1,
- 2 mg/100 μ L dose of ARS-1,
- placebo

To ensure proper wash-out between the IN doses, each subject will be randomized to one of the following sequences:

- 1 mg ARS-1 IN: placebo: 2 mg ARS-1 IN
- 2 mg ARS-1 IN: placebo: 1 mg ARS-1 IN

The side (right or left) of dosing will be alternated per randomization.

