4.1 Inclusion Criteria

For a subject to be eligible for this study, he or she must meet **all** of the following criteria:

1. Is a male or female subject between the ages of 18 and 65 years, inclusive.
2. Has been clinically diagnosed with acute flares or with chronic spontaneous urticaria with unknown etiology and have urticaria symptom (patient-rated pruritus and hive severity score ≥ 2) at least two (2) times a week while on a chronic treatment (e.g., antihistamine) at least 2 weeks before dosing and will remain the same throughout the study.
3. Has body weight more than 30 kg and body mass index between 18 and 34 kg/m², inclusive.
4. Has no medical history of hypertension and cardiovascular disease in the last 10 years. Controlled hypertension without beta blocker confirmed by the Investigator is acceptable.
5. At screening, has stable vital signs in the following ranges (after 5 minutes of rest):
 - SBP ≥ 90 and ≤ 140 mmHg
 - DBP ≥ 50 and ≤ 90 mmHg
 - HR ≥ 45 and ≤ 100 bpm

Note: Each BP should be taken after at least 5 minutes rest in a chair with back supported, legs uncrossed, and upper arm bared (slight recline for comfort is permitted). If vital signs are out of range, the Investigator may obtain two additional readings, so that up to 3 consecutive assessments are made within 1 hour.

6. If female, is not pregnant or breastfeeding based on the following:
 - a. agree to the use of highly effective contraceptive methods for at least 2 weeks before baseline until 7 days after the last day of study drug and a negative urine pregnancy test at screening; or
 - b. is of nonchildbearing potential defined as clinically infertile as the result of surgical sterilization (hysterectomy, bilateral tubal ligation, bilateral salpingectomy and/or bilateral oophorectomy); or

- c. is confirmed postmenopausal status (defined as either having amenorrhea for ≥ 12 consecutive months without another cause and documented serum follicle-stimulating hormone (FSH) level > 40 mIU/mL or another documented medical condition (e.g., was born without a uterus)).

NOTE: The following are considered highly effective contraceptive methods: abstinence, hormonal oral contraceptives, injectables, and patches; intrauterine devices; double-barrier methods (synthetic condom, diaphragm, or cervical cap used with spermicidal foam, cream, or gel); Nexplanon contraceptive implant (if implanted within 3 years); and male partner sterilization.

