- 7. If male (with or without vasectomy), agree to the use of highly effective contraceptive methods (as listed in Criterion #6 above) at screening until 7 days after the last day of study drug.
- 8. Is able to communicate clearly with the Investigator and staff; able to read, complete questionnaires, and understand study procedures.
- 9. Is willing and able to provide written informed consent prior to participating in the study.

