5.2 Medical History

A medical history will be obtained at screening. Medical history will include demographic data (age, sex, race/ethnicity, etc.). The medical history will be confirmed at pre-dose in Treatment Period 1.

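### Inclusion criterion 6a has two versions: the synopsis requires a pregnancy test at baseline, while the body schedules one only at screening, up to 90 days before the first dose

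*Combined protocol and SAP*

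**What the plan says.** The synopsis (Main Inclusion Criteria, 6a) makes eligibility depend on "a negative urine pregnancy test at baseline". The same criterion in Section 4.1 depends on "a negative urine pregnancy test at screening". Section 5.6.5, the Section 10.1 screening list, and the Appendix A row with its footnote all place the urine test at screening. Section 10.1 allows screening up to 90 days before dosing.

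Section 10.2 lists what is done before dosing in each period. It includes confirming eligibility and medical history in Period 1, but no pregnancy test. Section 5.2 likewise states: "The medical history will be confirmed at pre-dose in Treatment Period 1".

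Both versions of criterion 6 open with the general condition "If female, is not pregnant or breastfeeding based on the following". Both versions of 6a require the woman to "agree to the use of highly effective contraceptive methods for at least 2 weeks before baseline".

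**The concern.** A subject must meet every inclusion criterion, so the two versions of 6a can give different answers for the same woman. A site that follows Appendix A can dose someone who has not met 6a as the synopsis states it. When eligibility is confirmed at Period 1, one text calls for a new test and the other accepts a result that may be three months old.

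What is at stake is exposure to epinephrine in a pregnancy that began after screening, or was too early to detect then, and that the woman does not know of or does not report. The body text schedules nothing that would find it. The 24-hour pregnancy report in Section 13.3 comes only after exposure.

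**Working it through.** No figure in the plan needs reproducing. The check compares the texts and then does simple date arithmetic.

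**Where the test is placed**

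| Location | Timing of urine pregnancy test |
|---|---|
| Synopsis, criterion 6a | Baseline |
| Section 4.1, criterion 6a | Screening |
| Section 5.6.5 | Screening |
| Section 10.1 | Screening (Day -90 to Day -1) |
| Section 10.2, pre-dose list | None |
| Appendix A, row and footnote | Screening only |

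All of these entries are readable, so redaction does not explain the difference.

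**Could baseline mean screening?** The protocol gives no general definition, but its usage points the other way.

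- Section 5.5 names screening and baseline as separate ECG time points.
- Section 10.3 places the baseline safety assessments before randomisation and dosing in the treatment periods.
- Section 14.3.1 sets the baseline for the primary endpoints at pre-dose of each visit.
- Section 4.1 6a uses both words in one sentence: contraception is counted back from baseline, and the test is at screening.

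For an entry criterion, the natural reading of baseline is therefore Period 1 pre-dose.

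**Age of the test at dosing.** Let D be the number of days from the screening test to the first dose. Section 10.1 gives D from 1 to 90.

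- Body text: age at first dose = D, so 1 to 90 days.
- Synopsis, or a Period 1 pre-dose test: age at first dose = 0 days.
- The synopsis (Study Duration) gives a study period of 3 to 4 weeks, so at the last dose the test may be up to about 90 + 28 = 118 days old under the body text. That fits the stated participation of up to 120 days. With a Period 1 test the figure is about 28 days.

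**What the other safeguards cover.** The opening condition of criterion 6, the Period 1 eligibility and history checks, and the Section 11 provision for discontinuation before the first dose all act on what is known. They can stop a pregnancy that the woman reports. They cannot be relied on for one that is unrecognised or unreported. Contraception is required for at least 2 weeks before baseline, which need not cover the whole time since screening.

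**The case against.** The strongest reply is that the operative text is consistent. Sections 4.1, 5.6.5 and 10.1 and Appendix A agree, Section 10.1 sends sites to Section 4.0 for eligibility and to Appendix A for procedures, and only the synopsis differs. A slip in the synopsis is at least as plausible as a safety test lost from the body. This stands as far as intent goes: the documents do not show which version was meant. It does not remove the conflict. The text available contains no rule that the body prevails, and if the synopsis is the slip, the version that remains is the one without a test near dosing.

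A reader might infer three stronger points. The documents do not support resting the concern on any of them.

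- *Every first dose is active, so the risk is heightened.* The two sequences are "1 mg ARS-1 IN: placebo: 2 mg ARS-1 IN" and "2 mg ARS-1 IN: placebo: 1 mg ARS-1 IN", so the first dose is indeed always epinephrine. But both sequences give every completing subject both active doses. The order changes when exposure happens, not whether it happens.
- *Women may go 76 days with neither contraception nor a test required.* The arithmetic is 90 - 14 = 76, but that is a permitted ceiling. Dosing is triggered by a flare in subjects with symptoms at least twice a week, so shorter intervals are likely. A woman who cannot predict her dosing date must in practice already be using contraception in order to qualify when she presents.
- *Women's contraception should start at screening, because men's is required "at screening until 7 days after the last day of study drug".* The two versions of 6a agree on the contraception rule for women, so there is no conflict to repair. A Period 1 test already brings the interval since the last test to 0 days for every D. The change would add up to 76 days of required contraception for little gain.

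**Conclusion.** The inconsistency is real and should be corrected. As scheduled in the body, a woman of childbearing potential may be dosed on a pregnancy test up to 90 days old; as the synopsis has it, the test belongs to the dosing visit. This rests on reading baseline as Period 1 pre-dose, which the protocol's usage supports but does not formally define.

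The number of women exposed to the gap cannot be stated. The documents do not give the number of women of childbearing potential (assumed range 0 to about 32, the planned sample), the typical time from screening to dosing, or any pregnancy probability. The weight is therefore that of a low-cost correction for participant safety and consistent eligibility. Endpoints, sample size and analysis are unaffected.

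**What to change.** Use one wording in synopsis 6a and Section 4.1 6a: *a negative urine pregnancy test at screening and at Treatment Period 1 pre-dose*. Then:

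- in Section 5.6.5, add the Period 1 pre-dose test for women of childbearing potential, with the result read before dosing;
- in Section 10.2, add the test to the pre-dose list, marked Period 1 only;
- in Appendix A, mark the Period 1 pre-dose column of the pregnancy test row and amend the footnote to match.

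Section 10.1 and the contraception clause stay as they are.

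The cost is one urine strip per woman of childbearing potential, at most about 32 in all, at a visit where eligibility is already being confirmed. The synopsis already calls for a test at baseline, so this mainly brings the schedule into line with it. Testing again before Period 3 would be more complete, but Period 1 is a defensible minimum because contraception is already required until 7 days after the last dose.

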10.2 Pre-dose Evaluations (Treatment Periods 1 - 3)

Subjects will return to the site when experiencing an acute flare of urticaria symptoms or chronic spontaneous urticaria before taking other acute medications. Urticaria symptoms and severity will be assessed based on both patient-reported and clinician-based assessments. Pre-dose assessments include the following:

- Admission to clinical site
- Confirm eligibility (Treatment period 1 only)
- Confirm medical history (Treatment period 1 only)
- Targeted PE
- Concomitant medications
- Vital signs
- Patient-reported pruritus/hive score and VAS for pain
- Investigator-rated extent of urticaria and erythema score

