14.0 STATISTICAL CONSIDERATIONS

14.1 Sample Size Determination

The sample size is based on practical consideration. [REDACTED]

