14.3 Efficacy Data Analyses

14.3.1 Primary Efficacy Analyses

The baseline for the primary endpoints will be the pre-dose at each visit.

Superiority comparison of ARS-1 1 mg vs. placebo and ARS-1 2 mg vs. placebo at each timepoint will be tested at the two-sided 0.05 significance level. If both ARS-1 1 and 2 mg are statistically superior to placebo, comparison between the ARS-1 doses will be conducted.

Time to effect is defined to be the time that it takes to lower one grade, two grades, and three grades.

Duration of effect is defined as the time from when the grade becomes above baseline until the grade returned to baseline.

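### The efficacy model does not adjust for the pre-dose score taken before each spray, and the plan does not say whether the response is the raw score or the change from pre-dose

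*Combined protocol and SAP*

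**What the plan says.** The synopsis (Statistical Analysis) specifies, for all quantitative endpoints, "linear mixed models with fixed effects for treatment and period and a random effect for subject". It names two comparisons, each ARS-1 dose against placebo, makes no multiplicity adjustment and calls the analyses exploratory. Section 14.3.1 adds that "The baseline for the primary endpoints will be the pre-dose at each visit" and that each comparison, at each timepoint, "will be tested at the two-sided 0.05 significance level". It defines time to effect by grades lowered, and duration of effect by reference to baseline.

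Section 10.2 lists, among the pre-dose assessments of Treatment Periods 1 to 3, "Patient-reported pruritus/hive score and VAS for pain" and "Investigator-rated extent of urticaria and erythema score". Appendix A schedules the same assessments. The synopsis (Study Duration) states that "three acute flares of urticaria symptoms will be treated". Section 14.1 says "The sample size is based on practical consideration"; the planned number is 32, and the rest of that section is redacted, as is section 14.5.

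No visible text enters the pre-dose score in the model as a covariate, and none says whether the modelled response is the raw post-dose score or the change from pre-dose.

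**The concern.** A random subject effect removes only what is stable across a subject's three visits. Here the visits are three separate flares, and the subject arrives whenever one occurs. Inclusion criterion 2 asks for a history of symptoms scoring at least 2 twice a week. Section 10.2 confirms eligibility in Period 1 only, and no minimum pre-dose score is visible for a treatment visit. Pre-dose severity can therefore differ between the placebo visit and the ARS-1 visits of the same person. On the 0 to 3 itch and hive scales it also limits the possible improvement: a three-grade fall needs a starting score of 3.

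With 32 subjects, chance differences in flare severity add noise to the estimates and intervals, which are the main output of an exploratory trial. Leaving the response open also lets the choice between raw and change scores be made after the data are seen, and the two can differ considerably in precision.

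**Working it through.** There is no visible power calculation to reproduce, so the check compares the variance of three analyses.

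**Inputs.** From the documents: 32 subjects, three periods, the model terms above, and a pre-dose score in every period. Assumed: r, the within-subject correlation between pre-dose and post-dose score, and k, the pre-dose SD divided by the post-dose SD (both within subject). Within-subject post-dose variance is set to 1.

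**Formulas.**
- Raw post-dose score: 1
- Change from pre-dose: 1 + k² − 2rk, which is 2(1 − r) when k = 1 and 1.25 − r when k = 0.5
- Adjusted for pre-dose score: 1 − r², before the cost of estimating the slope

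The reduction against change scores is (k − r)² / (1 + k² − 2rk). With k = 1 this equals (1 − r)/2. It is zero when k = r.

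| r | Change, k = 1 | Adjusted | Reduction vs raw | Reduction vs change, k = 1 | Reduction vs change, k = 0.5 |
|---|---|---|---|---|---|
| 0 | 2.00 | 1.00 | 0% | 50% | 0.25/1.25 = 20% |
| 0.2 | 1.60 | 0.96 | 4% | 40% | 0.09/1.05 = 9% |
| 0.3 | 1.40 | 0.91 | 9% | 35% | 0.04/0.95 = 4% |
| 0.5 | 1.00 | 0.75 | 25% | 25% | 0/0.75 = 0% |
| 0.7 | 0.60 | 0.51 | 49% | 15% | 0.04/0.55 = 7% |

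**Cost.** With 32 × 3 = 96 observations, 96 − 32 = 64 degrees of freedom lie within subjects, and 64 − 2 − 2 = 60 remain after treatment and period. The period-specific pre-dose score takes one of these, and the subject mean takes one between subjects. Estimating the slope multiplies the variance by about 1.02, so the worst case against raw scores is √1.02 ≈ 1.01. Including this factor, the adjusted SE relative to the raw-score SE is 1.01, 0.99, 0.96, 0.87 and 0.72 at r = 0, 0.2, 0.3, 0.5 and 0.7. Relative to the change-score SE with k = 1 it is 0.71, 0.81, 0.87 and 0.93 at r = 0, 0.3, 0.5 and 0.7.

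**Simulation.** REML fits with 32 subjects, 1,200 runs per setting and k = 1. All six treatment orders were used with period in the model, so that the placebo contrasts exist. The entries are the empirical SD of the 1 mg vs placebo estimate.

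| Within r | Between r | Raw | Change | One pre-dose slope | Pre-dose split into subject mean and deviation |
|---|---|---|---|---|---|
| 0 | 0.8 | 0.253 | 0.346 | 0.259 | 0.254 |
| 0.2 | 0.8 | 0.254 | 0.319 | 0.256 | 0.252 |
| 0.3 | 0.5 | 0.249 | 0.288 | 0.236 | 0.237 |
| 0.5 | 0.5 | 0.245 | 0.253 | 0.216 | 0.216 |
| 0.7 | 0.7 | 0.254 | 0.199 | 0.184 | 0.184 |

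The rejection rate with no treatment effect was 0.040 to 0.060 for all four analyses. The subject-mean term avoids most of the small loss that a single slope shows when within- and between-subject correlations differ.

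**Estimability.** Section 3.1.1 lists two sequences, and both put placebo in period 2. Intercept, treatment and period then give 5 columns of rank 4, because the placebo indicator equals the period-2 indicator. Neither ARS-1 vs placebo contrast can be estimated. Adding the pre-dose score gives 6 columns of rank 5, and both contrasts remain inestimable.

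**The case against.** A reader might infer that the plan ignores the pre-dose score. It does not: section 14.3.1 makes it the baseline at each visit. What is missing is its role in the model.

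A reader might also infer a fixed gain, such as 32 subjects doing the work of 32/0.65 = 49, 32/0.75 = 43 or 32/0.85 = 38. The documents do not support those figures. They need a change-score response, which the plan never states, and equal variances. Equal variances are doubtful if subjects arrive in a flare with pre-dose scores near the top of a short scale. With the pre-dose SD at half the post-dose SD, the equivalents are about 33, 32 and 35. Against raw scores, a within-subject r of 0.2 or less gives almost nothing.

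A third inference is that omitting the covariate biases the comparison. Milder flares falling by chance on one treatment are sampling variation, already reflected in the standard error. Linear adjustment removes only the part that the pre-dose score predicts, and it does not model the cap on improvement.

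The strongest practical objection is that, with the sequences as listed and period in the model, adjustment cannot help either placebo comparison. That is correct, but it is a separate defect. Once it is resolved, the case for adjustment applies. The exploratory label lowers the stakes for error rates but does not remove the value of a stated response and tighter intervals.

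**Conclusion.** The point holds as one of precision and pre-specification. The model has no pre-dose covariate, the response is unstated, and the random subject effect does not capture severity that varies from flare to flare. The worst-case cost is small: about 1% on the SE relative to a raw-score analysis. The gain is conditional on r and on the variance ratio, neither of which is in the documents. It ranges from nothing to a 49% lower variance against raw scores (r from 0 to 0.7). Against change scores with equal variances it is 15% to 35% for r from 0.7 down to 0.3, and it is close to zero when the SD ratio is near r. Adjustment reduces the effect of chance imbalance in flare severity. It corrects no systematic bias, and type I error was near 5% with or without it. These figures treat the scores as continuous and require the placebo contrasts to be estimable.

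**What to change.** First reconcile the sequences in section 3.1.1 with the period term, since no covariate can separate placebo from period 2.

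Then, in section 14.3.1 and the synopsis, state the response and add two terms for each score endpoint that has a pre-dose value (pruritus/hive score, pain VAS, extent, erythema): that period's pre-dose score and the subject's mean pre-dose score. The model becomes response = treatment + period + period-specific pre-dose score + subject-mean pre-dose score, with a random subject effect. With the period's pre-dose score included, raw and change responses give the same treatment estimate, so the ambiguity no longer affects the comparison. Time to effect and duration of effect have no pre-dose value of their own and fall outside this change.

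The cost is one or two sentences and about 2 degrees of freedom. No new data are needed.
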